3.7 Trial Procedures

Table 3.7-1 summarizes the scheduled observations/tests and assessments.

Confidential - Proprietary Information

Table 3.7-1 Schedule of Observations/Tests and Assessments

Time Point	Screen	ning	Rı	ın-in Per	iod			Trea	tment Pe	riod		Follow-up
Item	Day-7 to -4	Day-4	Day-3	Day-2	Day-1	Dayl	Day2	Day3	Day4	Day5/ End of treatment	End-of-trial/At discontinuation (day after final administration)	Day 12 to 15/ 7 to 10 days after final administration
Informed consent												
Consent for DNA storage (optional)			0									
Subject demographics												
Inclusion/Exclusion criteria					•							
Confirmation of use of concomitant medications/ therapies	<											>
Subject registration,	_					•=	•					
randomization ^a												
Hospitalization		<									\rightarrow	
IMP administration							•					
Treatment compliance						←				\longrightarrow		
Use of diuretics (dose fixed)										-		
Plasma drug concentration (See Table 3.7-2)						•=	•	•	•	•	•	
Pharmacodynamics		ļ					!	l			ļ	Į.
Serum sodium and potassium						•=						
concentrations	_					•						-
Serum osmolality, biomarkers ^c						•					•	
Daily urine volume, daily fluid intake, urine sodium/potassium concentrations, urine osmolality			-	→ <	><	> ←	*	*	> <	*	\rightarrow	
Efficacy	1	ı	_		_		T _			I -		ı
Body weight	-		•	•	•	•	•	•	•	•	•	
Congestive symptoms ^g										•		
Chest X-ray ^h				■J								
NYHA Classification				■ ^j								
Safety												
AEs	<											
Clinical laboratory test						•					•	
Physical examination	•					•						
Vital signs d			•	•	•	•	•	•	•	•	•	
12-Lead ECG ^e				■ ^j								
Pregnancy test f	•											
Pharmacogenomics												
DNA Storage ⁱ						0						

- •, Mandatory (before breakfast and IMP administration [before breakfast on the day on which IMP administration is not scheduled]); •, Mandatory (at the specified time point)
- Optional (only applicable to the trial sites that have agreed to collect samples for DNA storage in advance. Samples for DNA storage will only be collected from subjects who have given written consent to DNA storage.)

Subjects are registered and randomized at screening and on Day 1, respectively, in the IWRS. Only the subjects who meet all the inclusion criteria (including the criteria specified in "Table 3.4.3-1 Criteria for Enrollment in the Treatment Period (Inclusion Criteria of Run-in Period)") and do not fall under any of the exclusion criteria are assigned to IMP administration. Randomization normally takes place on Day 1 (or Day -1 if justified. Each subject's fulfillment of inclusion criterion 8 will be verified on Day 1). Completion of the initial administration (Day 1), completion of blood sampling

^aSubject enrollment/randomization:

for plasma drug concentration measurement up to 24 hours after start of IMP administration on Day 1 (Day 2), and trial completion/discontinuation (end-of-trial/withdrawal) will be recorded in the IWRS.

^bTiming of blood sampling on Day 1 for measurement of serum sodium/potassium concentration:

Before IMP administration (before breakfast), between 4 and 6 hours after start of IMP administration, and between 8 and 12 hours after start of IMP administration. Measurement of serum sodium concentration during the treatment period takes place at the trial site in addition to at the central laboratory.

^cBiomarkers:

Plasma AVP concentration, plasma BNP concentration, plasma renin activity, serum NT-proBNP concentration, serum troponin concentration will be measured.

^dVital signs: Blood pressure, pulse rate, and body temperature will be measured.

^e12-lead ECG: Between 1 and 2 hours after start of IMP administration on Day 1 and Day 3. Subsequently when possible.

^fPregnancy test: Applicable to only female subjects of childbearing potential.

^gCongestive symptoms: Lower limb edema, other edema, jugular venous distension, pulmonary rales, third cardiac sound, hepatomegaly will be assessed.

hChest X-ray: Cardiothoracic ratio and pulmonary congestion will be assessed.

If the subject underwent chest X-ray at examination before participation in the trial, cardiothoracic ratio and pulmonary congestion may be assessed using the radiograph (must be taken within 14 days before consent) instead of obtaining a new one at the screening examination.

ⁱDNA storage: Blood will be collected before IMP administration on Day 1.

If blood cannot be collected at the above time point, collection may take place at any subsequent time point during the trial.

^j12-lead ECG, chest X-ray, and assessment for NYHA classification will each be conducted once during the run-in period.

Table 3	.7-2 Blood Sampling Schedule for Measurement	Plasma Drug Concentration		
	Sampling Time Point	Time Window		
Day 1	Before start of IMP administration	From 2 hours to immediately before start of IMP administration		
	1 hour after start of IMP administration	Within 5 minutes after end of administration		
	1.5 hours after start of IMP administration	Specified time point \pm 5 minutes		
	2 hours after start of IMP administration	Specified time point ± 5 minutes		
	4 hours after start of IMP administration	Specified time point \pm 20 minutes		
	6 hours after start of IMP administration	Specified time point \pm 30 minutes		
	12 hours after start of IMP administration	Specified time point ± 1 hour		
Day 2	24 hours after start of administration on Day 1 (and	22 to 24 hours after start of		
Day 2	before administration on Day 2)	administration on Day 1		
Day 3	24 hours after start of administration on Day 2 (and	22 to 24 hours after start of		
Day 3	before administration on Day 3)	administration on Day 2		
Day 4	24 hours after start of administration on Day 3 (and	22 to 24 hours after start of		
Day 4	before administration on Day 4)	administration on Day 3		
Day 5	24 hours after start of administration on Day 4 (and	22 to 24 hours after start of		
	before administration on Day 5)	administration on Day 4		
Day 6	24 hours after start of administration on Day 5	22 to 24 hours after start of administration on Day 5		

Confidential - Proprietary Information

3.7.1 Schedule of Assessments

3.7.1.1 Screening

After obtaining informed consent, the investigator or subinvestigator will assign a subject identifier to each subject according to Section 3.3.2 Subject Selection and Numbering. The date of consent and subject identifier will be recorded in source documents and CRF. The subject will then be registered in the IWRS. The IWRS will be used to monitor subject registration, etc. The use of the system will be described in a separate procedure.

After acquisition of informed consent, subjects will undergo the following screening (examinations/tests) between 7 days and 4 days before administration (Day –7 to Day –4) for eligibility assessment. The result of eligibility assessment will be recorded in source documents and CRF.

[Tests/Examinations]

Subject demographics [birth date, sex, height, nationality, race, ethnicity, underlying disease, heart failure subtype, presence/absence and type of arrhythmia, presence/absence of pacemaker, presence/absence of ICD, complications, and medical history], serum sodium concentration, serum potassium concentration, clinical laboratory tests, physical examination, vital signs (blood pressure, pulse rate, and body temperature), body weight, congestive symptoms, chest X-ray^{Note} (cardiothoracic ratio and pulmonary congestion), confirmation of use of concomitant medications and therapies, urine pregnancy test (only in female subjects of childbearing potential)

Note) If the subject underwent chest X-ray at examination before participation in the trial, cardiothoracic ratio and pulmonary congestion may be assessed using the radiograph (must be taken within 14 days before consent) instead of obtaining a new one at the screening examination.

3.7.1.2 Run-in Period (Day −3, Day −2, and Day −1)

The investigator or subinvestigator will perform the tests and examinations specified below to decide whether the subject is eligible for enrollment in the treatment period. The dose and regimen of the diuretics the subject is using at the start of the run-in period (on Day -3) will not be modified until the end-of-trial examination (or withdrawal examination), irrespective of prior use of diuretics and its administration methods before the run-in period.

Confidential - Proprietary Information

The subject will be hospitalized from the day before the run-in period to the end-of-trial (or discontinuation) examination.

(1) Each Day during Run-in Period (3 Days)

(a) Before breakfast

- Vital signs
- Body weight

(b) After breakfast

The subject will be asked to void his/her bladder immediately before breakfast to start pooling of urine and measurement of fluid intake for the following measurements:

- Daily urine volume
- Daily fluid intake
- Daily fluid balance (difference between daily fluid intake and daily urine volume)
- Daily urine sodium excretion and daily urine potassium excretion (calculated using urine sodium concentration, urine potassium concentration, and daily urine volume)
- Urine osmolality

(c) Administration of diuretics

(d) At an appropriate time point of the scheduled day

- Physical examination
- Congestive symptoms
- Confirmation of use of concomitant drugs and therapies
- AEs

(2) On 1 Day during the Run-in Period (3 Days)

Each will be performed/assessed once, when appropriate.

- 12-lead ECG
- Chest X-ray
- NYHA Classification

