3.2 Trial Treatments

3.2.1 Dose and Regimen and Duration of Treatment

The dose levels and formulations for each group are summarized in Table 3.2-1. The investigator or subinvestigator will administer either one tolvaptan 15-mg tablet or placebo tablet once a day with water, immediately followed by intravenous administration of either OPC-61815 injection at 2 mg, 4 mg, 8 mg, or 16 mg or placebo for 1 hour (acceptable range: 55 to 65 minutes) according to a separate written procedure for IMP administration. Each dose should be administered promptly after the patient completes urine sampling (for daily urine volume measurement) after breakfast each day during the 5-day treatment period. The time of administration (start time of administration) on Day 2 and later should be not more than 20 minutes before or after the time of administration (start time of administration) on Day 1. After confirming each

Confidential - Proprietary Information

34

dose has been administered, the investigator or subinvestigator documents the start and finish time of administration (for injection) or the date and time of administration (for tablet) in source documents and case report form (CRF). The IMP is to be administered even if the patient fails to eat breakfast that day.

Table 3.2-1 Dose Levels and Formulations per Group				
Group	OPC-61815 Dose	Formulation(s) (per day)		
Tolvaptan 15-mg tablet	0 mg/day	1 vial of placebo injection, 1 tolvaptan 15-mg tablet		
OPC-61815 injection 2 mg	2 mg/day	1 vial of OPC-61815 injection 2 mg, 1 placebo tablet		
OPC-61815 injection 4 mg	4 mg/day	1 vial of OPC-61815 injection 4 mg, 1 placebo tablet		
OPC-61815 injection 8 mg	8 mg/day	1 vial of OPC-61815 injection 8 mg, 1 placebo tablet		
OPC-61815 injection 16 mg	16 mg/day	1 vial of OPC-61815 injection 16 mg, 1 placebo tablet		

[Rationale for duration of treatment]

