3.7.1.8 Treatment Period (End-of-trial or at Discontinuation)

When the subject completes trial treatment on Day 5, he/she will undergo the tests and assessments specified below as the end-of-trial examination on Day 6. If the subject discontinues trial treatment prematurely before the duration of administration reaches 5 days (see Section 3.8.3.1 Treatment Discontinuation), he/she will be requested to undergo the same tests and assessments the day after the final IMP administration, if possible. Completion of the end-of-trial or withdrawal examination will be recorded in the IWRS.

(1) Before Breakfast

Plasma drug concentration (24 hours after start of IMP administration on Day 5)

- Serum sodium concentration, serum potassium concentration, serum osmolality, and biomarkers
- Clinical laboratory tests and vital signs
- Body weight

(2) Administration of Diuretics

(3) When Appropriate on the Day after Final Administration

- Physical examination
- 12-lead ECG
- Congestive symptoms
- Chest X-ray
- NYHA Classification
- Confirmation of use of concomitant drugs and therapies
- AEs

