8.3 Subgroup Analyses

Subgroup Analyses will not be performed in this trial.

9 Safety Analyses

The following analyses will be performed for each group (including the entire OPC-61815 group) in the safety analysis set.

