9.4 Vital Sign Data

Descriptive statistics will be calculated for vital signs together with the changes from baseline at each time point and after final administration.

9.5 **Electrocardiogram Data**

Descriptive statistics of each 12-lead electrocardiogram (ECG) parameter and the changes from baseline in each parameter at each time point and after final administration will be calculated.

The number and percentage of subjects who have a QTc interval (QTcB, QTcF) of “> 450 msec”, “> 480 msec”, and “> 500 msec” at at least one postdose time point or after final administration will be calculated. In addition, the number and percentage of subjects who show a change of “> 30 msec” and “> 60 msec” in QTc interval from baseline at at least one postdose time point or after final administration will be calculated. The numbers and percentages of subjects will also be calculated at baseline and each postdose time point in the same manner. “Normal” and “abnormal” assessments at each postdose time point and after final administration compared with baseline will be summarized in a shift table. “Normal” and “abnormal” assessments by the trial site (investigator or subinvestigator) will be used instead of the assessments by the central ECG analysis laboratory.

10 **Pharmacokinetic Analyses**

This section describes the pharmacokinetics of primary and secondary endpoints.

- 1) Endpoints
 - a) Primary Endpoint :
 - C_{max} and AUC_{24h} of plasma tolvaptan on Day 1 of treatment period
 - b) Secondary Endpoints:
 - i) Plasma concentrations of OPC-61815, tolvaptan, DM-4103 and DM-4107
 - ii) Plasma pharmacokinetic parameters of OPC-61815, tolvaptan, DM-4103 and DM-4107
 - Day 1 of treatment period: C_{max}^a , AUC_{24h}^a , AUC_t , AUC_{∞} , t_{max} , λ_z , $AUC_ \%Extrap$, t_{last} , $t_{1/2,z}$, CL^b , CL/BW^b , V_z^b , V_z/BW^b , CL/F^c , $CL/F/BW^c$
 - Day 1, Day 2, Day 3, Day 4, and Day 5 of treatment period: C_{24h}^d
 - Day 5 of treatment period: $R_{5,ac}(C_{24h})$

^aExcluding tolvaptan

^bCalculated only for OPC-61815 after administration of OPC-61815 injection

^cCalculated only for tolvaptan after administration of tolvaptan 15-mg tablet

^dFor calculation of descriptive statistics, C_{24h} will be handled as plasma concentrations.

iii) Ratio of the AUC of metabolite to that of OPC-61815^e

Day 1 of treatment period: AUC_{∞} , AUC_{24h} , and AUC_t

^eCalculated only for the OPC-61815 injection groups

2) Handling of Data

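### The one run-in ECG that serves as QTc baseline is not matched in clock time or meal state to the Day 1 and Day 3 ECGs, so within-arm QTc changes mix timing with any drug effect

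*Protocol*

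**What the plan says.** **Baseline.** Protocol 3.7.1.2 (2) lists the 12-lead ECG among tests done on one of the three run-in days: "Each will be performed/assessed once, when appropriate". No hour and no relation to meals is given. Neither the screening list (3.7.1.1) nor the Day 1 pre-dose list (3.7.1.4) contains an ECG, so this is the only reading before treatment. Protocol 7.6.4 and SAP 3.4 both use the run-in value as the ECG baseline.

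**Post-dose ECGs.** Footnote e to Protocol Table 3.7-1 sets the timing: "Between 1 and 2 hours after start of IMP administration on Day 1 and Day 3. Subsequently when possible". Under Protocol 3.2.1 the dose is given "promptly after the patient completes urine sampling (for daily urine volume measurement) after breakfast each day", with one exception: "The IMP is to be administered even if the patient fails to eat breakfast that day". The last ECG (Protocol 3.7.1.8) is scheduled "When Appropriate on the Day after Final Administration".

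**Analysis.** SAP 9.5 tabulates mean changes and counts patients with changes above 30 and above 60 msec "in QTc interval from baseline at at least one postdose time point or after final administration will be calculated". SAP Section 9 states: "The following analyses will be performed for each group (including the entire OPC-61815 group) in the safety analysis set". No between-group QTc contrast and no adjustment for time or meal is planned. The trial has no placebo arm (Protocol 2.1). Protocol 3.7.4.4 asks for the ECG date, not its time, in the CRF.

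**The concern.** A change score isolates treatment only if the two readings are otherwise comparable. Here the later readings on Days 1 and 3 fall in a narrow, usually fed, post-breakfast window, while the baseline may fall at any hour, fed or fasting. Any dependence of QTc on clock time or meals enters the change.

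Two features make this matter more. No arm is drug-free, so a within-arm change has no untreated reference. The arms are also small: with 11 patients, one case is 1/11 = 9% of an arm. Protocol 1.3 records that OPC-61815 had not been given to heart failure patients before, so absolute ECG changes will be looked at. The protocol pins down other baselines more closely: weight, vital signs and laboratory values are taken before breakfast on Day 1.

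**Working it through.** The documents give no QTc SD, no timing or meal effect and no QTc sample-size figure, so there is nothing to reproduce. What follows is an illustration.

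**Inputs from the documents.** One baseline ECG; three post-dose ECGs (Days 1, 3 and 6); threshold 30 msec; 11 patients per arm, 5 × 11 = 55 in all, of whom 4 × 11 = 44 receive OPC-61815.

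**Assumed inputs.** Independent normal errors with SD s = 10 msec per reading (8 and 12 as a range); no drug effect; an offset d on the Day 1 and Day 3 readings relative to baseline; no offset on Day 6, since both that ECG and the baseline are untimed.

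**Formula.** Given a standardised baseline error z, a patient has no change above 30 msec if all three later readings stay below the limit. So

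P(any change > 30) = 1 − ∫ φ(z) · Φ((30 − d)/s + z)² · Φ(30/s + z) dz.

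Numerical integration gives:

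| Offset d (msec) | s = 8 | s = 10 | s = 12 | Expected in 55 (s = 10) | P(at least 1 in an arm of 11) (s = 10) |
|---|---|---|---|---|---|
| −10 | 0.4% | 2.0% | 5.1% | 1.1 | 20% |
| −5 | 0.6% | 2.7% | 6.6% | 1.5 | 26% |
| 0 | 1.1% | 4.4% | 9.4% | 2.4 | 39% |
| +5 | 2.8% | 7.8% | 14.0% | 4.3 | 59% |
| +10 | 7.0% | 14.1% | 21.1% | 7.8 | 81% |

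Expected cases are 55 × P, for example 55 × 0.044 = 2.4. The last column is 1 − (1 − P)^11.

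**Random offset.** Uncontrolled baseline times would more plausibly give each patient a different offset. Averaging the formula over d ~ N(0, t²) at s = 10 gives 5.3% for t = 5 (55 × 0.053 = 2.9 cases) and 8.0% for t = 10 (4.4 cases). If the random offset arises in the baseline alone and so affects Day 6 too, the figures are 5.6% and about 9%.

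**Threshold of 60 msec.** Replacing 30 by 60 gives at most 0.04% at s = 10 and 0.33% at s = 12, both at d = +10. With the random offset at s = 10 it is below 0.1%.

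**Between arms.** An offset shared by all arms contributes d − d = 0 in expectation to OPC-61815 minus tolvaptan. A random offset leaves chance imbalance between two groups of 11 with standard error t × √(2/11): 5 × 0.426 = 2.1 msec and 10 × 0.426 = 4.3 msec.

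**The case against.** The strongest reply is that a concurrent reference exists. Five arms are randomised 1:1:1:1:1, double-dummy, on one ECG and dosing schedule, and SAP Section 9 reports them by group. A common shift cancels in expectation between arms and across the four doses. This stands. It does not rescue the outputs actually planned, which are within-arm changes and counts.

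A reader might infer that the plan counts timing shifts as drug-related QTc change. The documents do not support that. SAP 9.5 tabulates changes descriptively and attributes nothing; causality is an investigator judgement made for adverse events (Protocol 5.1). The risk lies in interpretation.

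A reader might also infer that the effect must be false positives. Nothing in the documents gives a direction, and a negative offset lowers the count and could hide a real change.

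Three further points stand in part:
- Post-dose ECGs are not always fed, because dosing goes ahead without breakfast. That is a stated exception and adds variation of its own.
- Recording follows the central ECG laboratory's method, which is not supplied and might set conditions. That laboratory's electronic report may also hold the recording time. The protocol's own schedule sets no time for the baseline.
- SAP 9.5 also reports absolute QTc above 450, 480 and 500 msec, which needs no baseline subtraction.

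**Conclusion.** The point holds as a cheap improvement. The baseline ECG is single and untimed, the Day 1 and Day 3 ECGs are tied to a normally post-breakfast dose, and the Day 6 ECG is untimed. Within-arm QTc changes and the counts above 30 msec cannot separate a drug effect from timing and meal differences.

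The size is unknown. With a reading SD of 10 msec and no drug effect, the count above 30 msec could run from about 1 to about 8 of 55 for systematic offsets of −10 to +10 msec, against 2.4 with none. With purely random offsets of SD 5 to 10 msec it is 2.9 to 4.4. The upper end needs every patient to shift by +10 msec. All of this rests on assumed SDs and offsets and on independent normal errors. The count above 60 msec is hardly touched. QTc is a descriptive safety summary, so the primary comparison of tolvaptan exposure is unaffected.

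**What to change.** In Protocol 3.7.1.2 (2) and Table 3.7-1, place the one run-in ECG on Day −1, after breakfast if eaten, at the clock time that corresponds to 1 to 2 hours after the planned Day 1 dosing time. In 3.7.1.8, take the Day 6 ECG at the same clock time. Keep the run-in ECG as the baseline in SAP 3.4, which needs no change.

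The cost is slightly less freedom for the site in timing two ECGs that are already scheduled in patients who are already in hospital; no recording is added. The limits should be understood. Meal state will still differ in a patient who skips breakfast on one of the days, and a single baseline reading keeps its own noise: under the same assumptions the 4.4% chance (2.4 of 55) remains after perfect matching.

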3.7.1.3 Randomization and Initiation of Treatment Period

(1) Assessment of Eligible for Enrollment in the Treatment Period

Whether or not the subject fulfills the criteria presented in Table 3.4.3-1 Criteria for Enrollment in the Treatment Period (Inclusion Criteria of Run-in Period) is decided based

on the use of diuretics, body weight, and congestive symptoms during the run-in period. The decision is entered into the IWRS.

(2) Assignment of Subjects to Treatments

The subject who fulfills the criteria for enrollment in the treatment period will be randomized to one of the 5 groups listed below for IMP administration in a double-blind manner. The investigator or subinvestigator will verify the drug number assigned on the IWRS.

- OPC-61815 injection 2 mg group
- OPC-61815 injection 4 mg group
- OPC-61815 injection 8 mg group
- OPC-61815 injection 16 mg group
- Tolvaptan 15-mg tablet group

3.7.1.4 Treatment Period (Day 1)

(1) Before IMP Administration (Before Breakfast)

- Plasma drug concentration (within 2 hours before IMP administration)
- Serum sodium concentration, serum potassium concentration, serum osmolality, and biomarkers
- Clinical laboratory tests and vital signs
- Body weight
- Blood sampling for DNA storage (The subject may or may not agree to DNA storage. The subject's consent to DNA storage will be obtained before blood sampling.)

(2) After Tests/Blood Sampling and After Breakfast

The subject will be asked to void his/her bladder immediately after breakfast to start pooling of urine and measurement of fluid intake for the following measurements:

- Daily urine volume, daily fluid intake, and daily fluid balance
- Daily urine sodium excretion and daily urine potassium excretion
- Urine osmolality

(3) IMP Administration

The investigator or subinvestigator will administer the IMP to the subject after verifying that the subject meets the inclusion criteria and does not fall under any of the exclusion criteria. The investigator or subinvestigator subsequently will record IMP administration in the IWRS.

(4) Administration of Diuretics

(5) Tests and Assessments

The investigator or subinvestigator will perform the tests described below.

Table 3.7.1.4-1 Tests on Day 1, Their Scheduled Time Points, and Blood Sampling Time Points After IMP Administration							
Sampi							
Item	Time Point	Time Window					
Plasma drug concentration	1 hour after start of IMP	Within 5 minutes after end					
	administration	of IMP administration					
	1.5 hours after start of IMP	Specified time point ± 5					
	administration	minutes					
	2 hours after start of IMP	Specified time point ± 5					
	administration	minutes					
	4 hours after start of IMP	Specified time point ± 20					
	administration	minutes					
	6 hours after start of IMP	Specified time point ± 30					
	administration	minutes					
	12 hours after start of IMP	Specified time point ± 1 hour					
	administration						
Serum sodium concentration,	4 to 6 hours after start of IMP						
serum potassium concentration	administration						
	8 to 12 hours after start of IMP						
	administration						
12-lead ECG	1 to 2 hours after start of IMP						
	administration						
Physical examination	When appropriate on Day 1						
Congestive symptoms	When appropriate on Day 1						
Confirmation of use of	When appropriate on Day 1						
concomitant drugs and therapies	-						
Treatment compliance	When appropriate on Day 1						
AEs	When appropriate on Day 1						

